We previously tested the hypothesis that adaptation to upward-shifting prisms, producing a downward recalibration in pointing, would reduce forward stepping time in patients with Parkinson's disease. The rationale for this approach was that, based on the results of Tilikete and colleagues, adaptation to upward-shifting prisms would shift the standing posture forwards. In a study of 16 patients we found that a single five-minute session of prism adaptation reduced forward stepping time by an average of 183ms (~10% reduction) [4]. Backward stepping time was unchanged, and a test of adaptation to downward-shifting prisms with control participants showed no effect on forward or backward stepping. This study provides proof-of-concept that prism adaptation can reduce forward stepping time in patients with Parkinson's disease using a laboratory-based measure of stepping.

2. Objectives and Hypotheses

Objective: To compare the effect of two weeks of twice-daily adaptation to upward prismatic shifts in the visual field vs. two weeks of sham adaptation on measures of posture and gait in patients with idiopathic Parkinson's Disease.

Hypotheses: Compared to patients who undergo sham prism adaptation, patients who complete two weeks of real prism adaptation therapy will show reduced stepping initiation times, greater displacement of the body over the feet during stepping initiation, and increased self-report of confidence while walking. We will also measure a number of other common clinical indicators to determine whether prism adaptation improves motor performance and postural responses to external perturbations.

3. Study Design

Describe all study procedures, materials, and methods of data collection:

The study will have a longitudinal, repeated-measures, between-subjects, double-blind, sham-controlled design. Thirty patients with idiopathic Parkinson's Disease will be randomly assigned to undergo two weeks of twice-daily sessions of adaptation to upward-shifting prisms, or sham adaptation (in which patients perform the same sensory-motor task while wearing goggles fitted with neutral lenses). Measures of posture and gait (see below) will be recorded in two sessions: pre- and post-treatment. Additional long-term follow-up will be obtained through questionnaires by mail at one week, one month and three months post-treatment. The timeline for the research sessions, intervention period and follow-up questionnaires are outlined in Figure 1.

Procedures:

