All data will be anonymized and analyzed using non-parametric and parametric standard tests using SPSS software. Statistical analyses will be performed with appropriate correction for multiple comparisons.

The endpoints will be the post-treatment clinical assessment session.

Scores for each of the outcome measured will be analyzed using two-by-two, repeated measures ANOVAs, with Group (sham, prism) and session (pre, post) as independent factors. In the case of the self-report measures, two-by-four repeated measures ANOVAs will be performed with Group (sham, prism) and session (pre, post, one-month, three-months) as independent factors. Post hoc analyses will be in the form of t-tests (or non-parametric equivalents), corrected for multiple comparisons. These tests will determine if prism adaptation improves performance to a greater extent than sham treatment. In addition, 95% confidence intervals will be constructed around mean performance for each group before and after sham or prism treatment to test whether the group performance deviates significantly from established normative data or diagnostic cut-offs (e.g., for the UPDRS).

5. Study Progress Monitoring

Note: appropriate monitoring may include periodic assessment of the following:

- data quality
- timelines
- recruitment and enrollment

Provide a description of the methods which will be used to determine the progress of the study, including periodic assessments of data quality, timelines, recruitment, and enrollment as appropriate:

We will check into using the psychiatry DSMB.

6. Risks & Benefits

Note: Risks may be physical, psychological, social, legal, economic, to reputation, or others.

a. Describe any potential risks, their likelihood and seriousness:

There is a minor risk that the treatment or assessment procedures will result in some fatigue or discomfort. This is expected to be short-lived, and would be no greater than that involved in patients' normal physical therapy. To minimize the risk of fatigue during the pre- and post-treatment assessments, patients will be provided with breaks between tasks as required. Prism adaptation has been used for studying sensory-motor integration in healthy individuals for over a century, and in the treatment of stroke patients with hemispatial neglect for over ten years. In this time there have been no reports of serious adverse effects.

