Yes, the study is based on the premise that a link between a genotype or a biomarker and a specific disease or condition is clinically useful in predicting the development of that specific disease or condition. **Please complete the [Genetic Research Form](#) and upload it to the ‘Supporting Documents’ page in Rapport.**

-OR -

Yes, the study is looking for an association between a genotype or a biomarker and a specific disease or condition, but at this point it is not clear if the genetic marker has predictive value. The uncertainty regarding the predictive value of the genetic marker is such that studies in this category will not involve referral of participants to genetic counseling; however, participants will be informed of genetic testing in the consent form. **Please comment:**

10. Equitable Participant Selection

a. Estimated number of participants at Dartmouth CPHS reviewed sites:

Approximately 30 patients will be enrolled in the study at Dartmouth-Hitchcock Medical Center.

b. Provide a justification of the proposed sample size

For the methods specified above, there is no well-established method for calculation of group size as yet. We can, however, draw on experience from previous experiments, indicating what is the minimal/optimal number of participants for detecting significant effects. Previous studies that tested the effects of a similar prism adaptation treatment protocol on sensory and motor problems in stroke patients have used between 12 and 16 patients per group (Frassinetti, Serino). We aim to approach 40 patients with at least 32 completing the study (16 per group), which will provide a sufficient dataset even if up to 20% of participant withdraw before the completion of the study

c. Define the target population:

The patient population that will be targeted are the patient is referred for Parkinson's disease with gait impairment at Dartmouth-Hitchcock Medical Center

Inclusion/Exclusion Criteria:

Inclusion

- Diagnosis of idiopathic Parkinson's Disease
- Referral for gait training
- Aged 40-85
- If the subject is taking CNS-acting CNS-acting medications (benzodiazepines, hypnotics, antidepressants), regimen must be stable for 30 days prior to baseline visit
- Subjects with Stage II.5 – Stage IV (Hoehn and Yahr scale) where stage II.5 is bilateral involvement with axial involvement, but without balance difficulty, to Stage IV where one has severe disability but is still able to walk or stand unassisted.

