- Subjects with any of the following abnormal scores (greater than 0) in the MDS-UPDRS Part III:
a) Part III.10 Gait; b) Part III.11 Freezing of gait c) Part III.12 Postural Stability
- Subjects with a Timed up and go test > 12 seconds

- Right-handed participants are preferred due to the cortical lateralization of functions related to sensorimotor adaptation and postural control. However we will recruit left-handed participants if there are insufficient right-handed volunteers.

Exclusion

- Subjects with a known psychiatric comorbidity that in the investigator's opinion would compromise participation in the study
- Subjects with a neurologic diagnosis, other than Parkinson's disease that can cause imbalance and gait impairment. (e.g., multiple sclerosis, stroke, subdural hematoma, peripheral neuropathy)
- Injury or impairment to the right arm (other than that which is due to Parkinson's Disease) that would affect pointing movements
- Subjects with normal score on UPDRS part III
- Classified as legally blind or lacking sufficient visual acuity to view the target and pointing hand during prism adaptation.
- Lacking sufficient understanding of verbal and written information in English to complete any of the consent screening forms

d. Vulnerable populations

Note: Certain populations are considered vulnerable to coercion and undue influence and are provided with additional protections when participating in a research study.

Identify any of the below populations which you plan to recruit for this study. In addition, complete the form(s) linked with each population as necessary and upload on the 'Supporting Documents' page in Rapport.

- [Pregnant Women, Fetuses and Neonates](#)
- [Children](#)
- [People with impaired decision-making capacity](#)

The following populations may also be considered vulnerable to coercion or other undue influence:

- Prisoners
- People who are economically disadvantaged
- The elderly
- People who are illiterate or do not speak English
- Students and employees

Describe any other potentially vulnerable population(s) and the additional protections provided to them:

Not applicable. We will be recruiting the elderly but will not be excluding people regarding socioeconomic status.

11. Recruitment

Describe method(s) of recruitment. Associated advertisements and other materials to be used for recruitment should be uploaded to the 'Consent Forms and Recruitment Materials' page in Rapport.

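### The plan's only confidence intervals test each arm separately against norms; the prism-minus-sham difference, which is the objective, gets neither an estimate nor an interval.

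*Combined protocol and SAP*

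**What the plan says.** Section 2 states the objective as a comparison of two weeks of prism adaptation with "two weeks of sham adaptation on measures of posture and gait in patients with idiopathic Parkinson's Disease".

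Section 4 says that scores will be "analyzed using two-by-two, repeated measures ANOVAs, with Group (sham, prism) and session (pre, post) as independent factors"; the self-report measures get a two-by-four version. It continues: "Post hoc analyses will be in the form of t-tests (or non-parametric equivalents), corrected for multiple comparisons". It then says what this analysis is for: "These tests will determine if prism adaptation improves performance to a greater extent than sham treatment".

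The next sentence is introduced as an addition and is the only mention of confidence intervals in the document: "95% confidence intervals will be constructed around mean performance for each group before and after sham or prism treatment". Their stated use is "to test whether the group performance deviates significantly from established normative data or diagnostic cut-offs", with the UPDRS as the example. No estimate or interval for the difference between groups is specified anywhere.

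Two other places bear on the point. Section 10b gives the planned size: "We aim to approach 40 patients with at least 32 completing the study (16 per group"). Section 10c lists among the inclusion criteria "Subjects with a Timed up and go test > 12 seconds" and an abnormal gait, freezing or postural stability item of UPDRS Part III, and it excludes patients whose Part III score is normal.

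**The concern.** The trial exists to estimate one contrast, prism against sham, yet the plan promises precision only for quantities that do not answer that question. The contrast itself is promised only as tests. Section 10b gives no power calculation, so an interval is the main means of telling an absent effect from one that the trial was too small to resolve. A bare non-significant p-value would hide that.

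The norm tests bring a second problem. They are run in each arm at each assessment, so a pair of verdicts such as prism no longer differing from the norm while sham still does is a possible output of the plan. That pair compares two significance results and does not measure the difference between the arms. It can arise with no treatment effect. A group can also lose its significant deviation merely because its interval is wide.

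**Working it through.** **The plan's own figure.** The only derivable number in Section 10b is the 40 patients to approach: 32 / (1 − 0.20) = 40. It reproduces. No effect size, SD, power or interval width is stated, so the results below are in SD units. The distances from a norm and the pre-post correlations are assumptions.

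**Inputs.** n = 16 completers per group (Section 10b); 95% intervals (Section 4); the norm treated as a fixed value; normally distributed scores.

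**Step 1: width of a single-group interval.** Half-width = t(0.975, n−1) / √n. At n = 16 this is 2.131 / 4 = 0.53 SD. Sections 3 and 10a speak of about 30 patients. If 20% of 30 withdrew, 24 would remain, or 12 per group, and the half-width would be 2.201 / √12 = 0.64 SD.

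**Step 2: split verdicts with no treatment effect.** Let both arms have the same true mean, d SD from the norm. Let p be the probability that one arm's interval excludes the norm (noncentral t, 15 degrees of freedom, noncentrality d√16). The arms disagree with probability 2p(1−p). The pattern favouring prism has probability p(1−p).

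| d (SD, assumed) | p | Arms disagree | Favours prism |
|---|---|---|---|
| 0 | 0.050 | 9.5% | 4.7% |
| 0.25 | 0.155 | 26% | 13% |
| 0.5 | 0.465 | 50% | 25% |
| 0.75 | 0.801 | 32% | 16% |
| 1.0 | 0.962 | 7% | 4% |

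The expression 2p(1−p) cannot exceed 50%, so the row at 0.5 SD is essentially the maximum.

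**Step 3: the pre/post version.** This used 100,000 simulated trials per setting, n = 16 per group, the same true change in both arms, and pre-post correlation 0.5 or 0.8. The pattern counted is that both arms differ from the norm at baseline, and afterwards only sham does.

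- Both arms move from 1.0 to 0.5 SD: about 23% of trials.
- Both move from 1.0 to 0.75 SD: 13–14%.
- Both stay at 0.75 SD: 5–8%.

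A direct between-group test on change rejected in about 5% of the same trials.

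**Step 4: the interval that serves the objective**, at n = 16 per group, in baseline SDs, with the same SD at both visits:

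- Unadjusted difference in change: t(0.975, 30) × √(2(1−ρ)) × √(2/16), with t = 2.042.
- Baseline-adjusted difference (ANCOVA): t(0.975, 29) × √(1−ρ²) × √(2/16), with t = 2.045.

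| ρ (assumed) | Unadjusted change | Baseline-adjusted |
|---|---|---|
| 0.5 | 0.72 | 0.63 |
| 0.7 | 0.56 | 0.52 |
| 0.8 | 0.46 | 0.43 |

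**The case against.** The strongest reply is that the plan already contains a direct between-group test and says that this test settles efficacy. The norm intervals come afterwards as a supplement. This stands. A reader might infer that the plan means to judge efficacy by comparing two within-group verdicts, but Section 4 says otherwise.

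A reader might also infer that every baseline norm test has its answer fixed by eligibility. The documents do not support that. The entry criteria on outcome measures touch only Timed Up and Go and UPDRS Part III. They leave open the Functional Gait Assessment, the mechanized measures and the questionnaires. Nor does the plan say that 12 seconds is the cut-off to be used in the analysis.

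The 50% figure should not be read as a typical rate, because it is a ceiling reached at one assumed distance. Where every patient lies beyond a cut-off and nothing changes, the group mean is likely to sit well past it. With an exponential or half-normal excess over the cut-off (an illustrative assumption), opposite verdicts occur in under 0.2% of simulated trials. Equal improvement in both arms raises the rate again, as Step 3 shows.

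Finally, it can be said that an interval for the difference is easily had from the planned analysis. That is true of the unadjusted difference in change, but the plan does not commit to reporting it. The baseline-adjusted difference needs a different model, since the two-by-two ANOVA has no baseline covariate.

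**Conclusion.** The point holds as a gap in what will be estimated and reported, and the plan should be changed. It does not show a planned false efficacy claim. The only intervals are placed on single-group means and used as tests, while the contrast in the objective is promised only as tests, in a trial without a power calculation.

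The risk of misreading runs from 7% to 50% of trials with split verdicts under equal true means, for assumed distances of 0.25 to 1.0 SD at 16 per group. Half of these favour prism. The documents give no distance from any norm, so where a given outcome falls in that range is unknown. The statement that non-significance does not show normal performance needs no assumed distance: the interval reaches 0.53 SD either side of the mean. The missing interval for the difference stands however the norm tests are read.

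**What to change.** Replace the confidence-interval sentence in Section 4 with wording such as: For each outcome measured before and after treatment, the prism-minus-sham difference in the post-treatment score, adjusted for the baseline score by ANCOVA, will be reported with its 95% confidence interval. Group means with 95% intervals will be shown beside norms or cut-offs for description only. A different result in the two groups against a norm is not evidence of a treatment effect, and an interval that includes a norm is not evidence of normal performance.

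Add that baseline Timed Up and Go and UPDRS Part III will not be tested against thresholds used for eligibility.

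The cost is one simple extra model per outcome, with no new data or visits, and the loss of the formal within-group tests against norms. The clinical context that the norms give is kept.

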MINIMAL RISK CLINICAL RESEARCH PLAN

Please complete: CPHS#

PI: [name] MD PhD

[name]

Important Note: The CPHS Department (Chair & Scientific) Review Form is required with this application. Find the form in the RAPPORT Library or on the CPHS Website.

- Respond to each item, even if to indicate N/A or not applicable
- Attach and/or upload this form as your 'Investigator Protocol' in Rapport
- If you are completing this form on a Mac, indicate your answer to any checkboxes by bolding or highlighting, or by deleting any incorrect options.

1. Introduction and Background

Patients with Parkinson's disease experience impairments in the initiation and maintenance of walking, with decreased walking speed; small, shuffling steps; and 'freezing'. These gait impairments have been related to an inability to tilt the body forward enough to provide sufficient forward propulsion (Martin, 1963). In a previous study we demonstrated that the forward stepping times of patients with Parkinson's Disease were reduced following a five minute period in which they performed a simple non-invasive motor-training intervention called prism adaptation. Building on this proof-of-concept data, the present study will examine whether prism adaptation is a clinically viable rehabilitation tool for gait impairment. Using a double-blind, sham-controlled, randomized control design, we will examine whether consecutive daily sessions of prism adaptation for two weeks improves posture and gait in patients with idiopathic Parkinson's Disease. Forty patients will be randomly allocated to undergo either real or sham prism adaptation twice a day for two weeks. Posture and gait will be assessed before and after the intervention period using three sets of outcome measures: 1) standard clinical assessments, 2) Mechanized measurements and 3) self-report questionnaires. We hypothesize that, compared to patients who undergo sham prism adaptation, patients in the real prism adaptation condition will show reduced stepping initiation times, greater displacement of the body over the feet during stepping initiation, and increased self-report of confidence while walking.

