Randomization and blinding

[name] will oversee the allocation of the participants to the control or treatment group and will be the only researcher who will not be blinded as to the experimental condition to which each participant belongs.

Participants will be allocated to the control or treatment group according to a pre-generated sequence of pseudorandom numbers, although deviations from this sequence may be made in order to ensure that the two groups are approximately matched in severity of symptoms. After prism adaptation training [name] will give the participant the set of goggles that they will be using for their sham/real prism adaptation treatment. The goggles will be handed to the participant in a sealed, opaque bag so that none of the other researchers will be able to see what kind of goggles the participant has been given. The participant will be instructed to seal the goggles in the same bag when they bring them back to the Dartmouth Hitchcock Medical Centre at the end of the treatment period. [name] will not be involved in any of the pre- or post-treatment assessments. In order to gauge progress an initial analysis will be performed once 60% of the participants have completed the post-treatment assessment, in which case the other researchers will be unblinded as to the group membership of the participants who have already completed the main components of the study. Aside from [name], the remaining members of the research team will be blind as to the group membership of the remaining 40% of participants.

Prism adaptation

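### The plan randomises 40 patients in one section and 30 in another, and 30 cannot yield the stated minimum of 32 completers

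*Combined protocol and SAP*

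**What the plan says.** Four places in the combined protocol and SAP give a number of patients.

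- Section 1, Introduction and Background: "Forty patients will be randomly allocated to undergo either real or sham prism adaptation twice a day for two weeks".
- Section 3, Study Design: the sentence that opens "Thirty patients with idiopathic" goes on to assign those patients at random to real or sham adaptation.
- Section 10a, estimated number of participants: "Approximately 30 patients will be enrolled in the study at Dartmouth-Hitchcock Medical Center".
- Section 10b, sample size justification: "We aim to approach 40 patients with at least 32 completing the study (16 per group"), said to be sufficient "even if up to 20% of participant withdraw before the completion of the study".

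Section 10b makes no power calculation. Its basis is precedent: earlier studies of a similar treatment in stroke patients "have used between 12 and 16 patients per group".

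One other provision depends on the total. Under Randomization and blinding in section 3, "an initial analysis will be performed once 60% of the participants have completed the post-treatment assessment", and the other researchers are then unblinded to the patients who have finished.

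**The concern.** Sections 1 and 3 both describe the random allocation of patients in the same trial, yet one says 40 and the other 30. Both are current text. Section 10b fits only the larger number, because a trial cannot have more completers than it randomises.

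Three things depend on the answer. Section 10b offers no calculation of power or precision, so the count per group is the whole justification, and the Study Design section cannot deliver it. The ethics committee has been told about 30, so randomising 40 would exceed the declared figure and stopping at 30 would miss the completer target. The 60% analysis is triggered by a fraction of an unsettled total. With the total open and an unblinded look planned, nothing in the text prevents the final number from being settled after group results have been seen. Nothing suggests that this is intended.

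**Working it through.** **Inputs, all from the plan.** Randomised: 40 (section 1) or 30 (section 3). Enrolled: about 30 (section 10a). Completers: at least 32, 16 per group (section 10b). Withdrawal: up to 20% (section 10b). Precedent: 12 to 16 per group (section 10b). Initial analysis: at 60% of participants (Randomization and blinding).

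**Reproducing the plan's figure.** Completers = randomised × (1 − withdrawal).
- 40 × (1 − 0.20) = 32, or 16 per group.
- In reverse, 32 / 0.80 = 40.

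The arithmetic in section 10b is therefore right if 40 patients are randomised. Its verb is approach, but its calculation needs randomise: patients who are approached and decline are not withdrawals.

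**The same calculation with 30 randomised.**

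| Withdrawal | Completers | Per group | Shortfall against 32 |
|---|---|---|---|
| 0% | 30 × 1.00 = 30 | 15 | 2 (2/32 = 6%) |
| 20% | 30 × 0.80 = 24 | 12 | 8 (8/32 = 25%) |

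Reaching 32 from 30 would need retention of 32/30 = 106.7%, which is impossible.

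**The 60% analysis.** 0.6 × 30 = 18 and 0.6 × 40 = 24.

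**Declared enrolment.** 40/30 = 1.33, so the declared figure rises by a third if 40 is meant.

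**What the shortfall could cost (illustration only).** The plan states no alpha, power or standard deviation. I assume a two-sample t-test on pre-to-post change, which corresponds to the group-by-session comparison in the two-by-two ANOVAs, with 80% power, and solve with the noncentral t distribution. Section 4 says "Statistical analyses will be performed with appropriate correction for multiple comparisons" without giving a method, so two-sided alpha 0.01 serves as an assumed stand-in for a corrected level.

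| Completers per group | Detectable difference, alpha 0.05 | Detectable difference, alpha 0.01 | Power for 1.024 SD, alpha 0.05 |
|---|---|---|---|
| 16 | 1.024 SD | 1.280 SD | 80% |
| 15 | 1.060 SD | 1.327 SD | 77% |
| 12 | 1.197 SD | 1.511 SD | 67% |

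The 1.024 SD in the last column is simply what 16 per group could detect under these assumptions. The plan does not name it as a target.

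**The case against.** The natural way to reconcile the figures is to read 40 as the number approached and 30 as the number enrolled. That fails twice: section 1 says the forty are randomly allocated, and 32 completers still exceeds 30 enrolled. Leaning on the approximate wording in section 10a does not help either. That entry is only an estimate on a form, and section 3 states thirty without qualification. Even 32 enrolled would meet the target only if nobody withdrew.

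A stronger point is that 30 randomised gives 12 to 15 per group, within the precedent that is the plan's only evidence of sufficiency. This stands. The plan misses its own target at 30, but nothing in it shows that the trial would be inadequate at that size.

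Two further limits also stand. The power figures rest wholly on assumed inputs, and the step from 16 to 15 per group is small. The 20% is a planning allowance and guarantees nothing: if each patient independently had a 20% chance of withdrawing (an assumption), 40 randomised would reach 32 completers about 59% of the time, and 30 would reach 24 about 61% of the time.

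Finally, the plan attaches no stopping rule or alpha spending to the 60% analysis. The unsettled total therefore changes when unblinding happens and for how many patients, but not a stated decision rule.

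**Conclusion.** The concern holds, and the plan must be corrected. The number randomised has two values, 40 and 30, that nothing in the document reconciles. The minimum of 32 completers is consistent with 40 and impossible with 30. With 30 randomised, the plan falls 2 completers short with no withdrawals and 8 short at its own 20% allowance. This conclusion uses only the plan's figures and does not depend on the power illustration. It is a contradiction between sections, not a miscalculation in section 10b, and it does not establish that 30 patients would be too few.

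**What to change.** Choose one number randomised and state it in sections 1, 3, 10a and 10b, with randomise in place of approach in section 10b.

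- **If 40:** change the figure of thirty in section 3 and the enrolment in section 10a. The completer target in section 10b can stay, worded as conditional on withdrawal not exceeding 20%.
- **If 30:** change the figure of forty in section 1. In section 10b, replace the target with at least 24 completers (12 per group) provided withdrawal does not exceed 20%, and note that 12 is the lower end of the cited range.

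In either case, state the trigger for the initial analysis under Randomization and blinding as a count: 24 of 40 or 18 of 30. Optionally, add to section 10b a detectable difference for the two-by-two ANOVA outcomes, with alpha, power and the multiplicity correction stated as assumptions.

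The cost is mostly wording. Choosing 40 raises the enrolment declared to the ethics committee from about 30 to 40. Choosing 30 lowers the planned completers from 32 to 24.
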